17.3 Statistical Analysis Plan

The statistical analysis plan is described below. Unless otherwise stated, continuous variables are summarized by number of participants, mean and its standard deviation, minimum value, 25% percentile, median value, 75% percentile, and maximum value, while categorical variables are summarized by the number and percentage of participants in each category.

17.3.1 Demographic and Other Baseline Characteristics, and Severity of Primary Disease

Demographic and other baseline characteristics and severity of primary disease will be summarized, or the summary statistics will be calculated on the FAS.

17.3.2 Efficacy Analysis

This study will be conducted to evaluate the efficacy of nemolizumab in SSc patients with moderate to severe skin thickening in an exploratory manner.

- 1) Analysis of the primary endpoint: Change from baseline in mRSS at Week 24
Summary statistics will be calculated for mRSS at Week 24 and the change from baseline.
- 2) Summary of continuous data
The following analyses will be performed on the FAS:
 - Summary statistics will be calculated for the following variables and indicators at each time point.
 - The scores or measurements of the following variables will be used to create a spaghetti plot for each participant

Variable	Indicator
mRSS	Score
Physician's Global Assessment	Changes from baseline
Patient 's Global Assessment	Percent change from baseline
HAQ-DI	Score or measurement
FACIT-Fatigue	Change from baseline
FSSG	
FVC	
% FVC	
DLco	
%DLco	
TLC	
FEV ₁	
The number of digital ulcers	
ACR-CRISS (Only Week 12, 24 and 52)	Score
Severity Classification of Lung Lesion (Figure 10-1)	

ACR CRISS is calculated using the following formula.:

$$\frac{\exp(-5.54 - 0.81 \times \Delta_{\text{mRSS}} + 0.21 \times \Delta_{\text{FVC}\%} - 0.40 \times \Delta_{\text{pt-glob}} - 0.44 \times \Delta_{\text{MD-glob}} - 3.41 \times \Delta_{\text{HAQ-DI}})}{1 + \exp(-5.54 - 0.81 \times \Delta_{\text{mRSS}} + 0.21 \times \Delta_{\text{FVC}\%} - 0.40 \times \Delta_{\text{pt-glob}} - 0.44 \times \Delta_{\text{MD-glob}} - 3.41 \times \Delta_{\text{HAQ-DI}})}$$

Δ_{mRSS} : mRSS change

$\Delta_{\text{FVC\%}}$: Percent FVC change

$\Delta_{\text{pt-glob}}$, $\Delta_{\text{MD-glob}}$: Patient's / Physician's Global assessment change (cm)

$\Delta_{\text{HAQ-DI}}$: HAQ-DI Score change

The score of participants occurring any of the following events is 0:

- Onset of scleroderma renal crisis
- Decline in FVC% $\geq 15\%$ (requiring reevaluation within 1 month), and %FVC of 80% or less
- Onset of left ventricular failure requiring treatment (defined as left ventricular ejection fraction $\leq 45\%$)

*

- Onset of pulmonary arterial hypertension requiring right heart catheterization *

*Caused by SSc

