1.1.2 Therapeutic treatment of systemic sclerosis and its issues

The etiology of SSc has not been clarified, and the main treatment methods are symptomatic treatments and disease-modifying drugs that inhibit disease progression. The progression and sites of involvement of SSc are different for each patient, and accordingly, the treatment method is selected based on the symptom of each patient.

Diagnostic Criteria, Severity Classification and Guidelines of Systemic Sclerosis⁷⁾ state that oral corticosteroids are thought to be empirically valid for patients with progressing skin thickening at an early stage but that they have risk factors for inducing renal crisis. Cyclophosphamide is the most recommended treatment option for both skin thickening and interstitial lung disease in patients with SSc; however, it has a problem of difficulty in long-term administration because of its carcinogenicity, immunosuppression, and side effects of drug such as hemorrhagic cystitis. Other drugs for SSc symptoms are prostacyclin, endothelin receptor antagonists, and phosphodiesterase-5 inhibitors for the treatment of pulmonary hypertension, calcium channel blockers for the treatment of cardiac involvement, intravenous prostaglandin E1 or prostacyclin for the treatment of disturbed blood flow in the fingers, and proton pump inhibitors for the treatment of reflux esophagitis. However, due to limited efficacy or safety issues of these therapeutic agents, the disease burden remains high and there is a great unmet medical need.

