2.2 Secondary Objective

To evaluate the safety and pharmacokinetics of nemolizumab in SSc patients with moderate to severe skin thickening

3. Study Design

This is a phase II, single-arm, multiple-dose study consisting of a pre-treatment observation period (1-4 weeks) and a treatment period (52 weeks). The pre-treatment observation period is from the day of screening to the day of study treatment initiation, and participants will visit the site a total of twice, for screening and for study treatment initiation. The treatment period is from the day of study treatment initiation to Visit 17 (Week 52), during which participants will visit a total of 15 times: Week 1, 2 and 4, and every four weeks thereafter. Participants having received study treatment will be followed up 84 days after the day of the last dose of study treatment. Follow-up period is from Visit 17 (Week 52) or the day of discontinuation visit to the day of follow-up visit.

[figure not shown]
Study phase: Phase II

Study type: Open-label, single-arm, multiple-dose study

Participants: SSc patients with moderate to severe skin thickening

Target Sample Size: 8 participants

Figure 3-1: Study Schema

1) Pre-treatment observation period

The investigator or subinvestigator will make observations and assessments at the screening visit specified in [Table 9-1](#) after obtaining informed consent from the participant.

2) Treatment period

The investigator or subinvestigator will administer the investigational product (IP) (nemolizumab, 60 mg/body) every 4 weeks (Q4W) at visits until Week 48 after making observations and assessments on the day of study treatment initiation specified in [Table 9-1](#). In addition, the investigator or subinvestigator will make perform observations and assessments at each visit specified in [Table 9-1](#).

3) Follow-up period

All participants having received the IP will be scheduled to visit for follow-up 12 weeks after the day of the last dose of study treatment (the day of follow-up visit). On the day of the follow-up visit, the investigator or subinvestigator will evaluate the safety and efficacy after completion of study treatment for all participants.

4. Target Indication and Inclusion and Exclusion Criteria for Participants

The investigator or subinvestigator will ensure before enrollment that all inclusion criteria are met and none of the exclusion criteria are met.

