5.1 Discontinuation criteria

- 1) Use of other antibody drugs by Week 52 visit
- 2) Use of live vaccines by Week 52 visit
- 3) The investigator or subinvestigator determined that an adverse event which would prevent the continuation of the study has occurred.
- 4) The participant is found to fail to meet any of the inclusion criteria or to meet any of the exclusion criteria.
- 5) The participant is found to be pregnant.
- 6) The investigator or subinvestigator has determined that the participant should be withdrawn from the study due to inadequate response to the IP.
- 7) The participant requests to withdraw from the study.
- 8) The participant no longer visits the medical institution, and the study cannot be continued
- 9) The participant has died.
- 10) The sponsor has determined the participant discontinuation from the study due to significant protocol deviations.

The sponsor has prematurely terminated the study.

The investigator or subinvestigator has determined to withdraw the participant from the study for any other reasons.

• Rationale for discontinuation criteria

1) to 3), 5)	Established considering the safety of the participants
4)	Established because the participants are considered ineligible for the study
6)	Established to reduce disadvantages for the participants

7)	Established because it is considered the rights of participants
8) to 11)	Established for contingencies
12)	Established to allow participant discontinuation from the study at the discretion of the investigator or subinvestigator.

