8.4.3 Prohibited Concomitant Medications and Therapies

Concomitant use of medications and therapies listed below is prohibited in this study.

- From the day of study treatment initiation to Week 52 or to the physical examination on the day of visit for discontinuation
- 1) The following systemic medications:
 - a) Antifibrotic drugs (e.g., pirfenidone, nintedanib)
 - b) Immunosuppressants (e.g., cyclophosphamide, cyclosporine, tacrolimus, azathioprine, mycophenolate mofetil, mizoribine, sulfasalazine, leflunomide, methotrexate, hydroxychloroquine, D-penicillamine, sirolimus)
 - c) Tyrosine kinase inhibitors (e.g., imatinib)
 - d) JAK inhibitors (e.g., tofacitinib, upadacitinib)
 - e) Endothelin receptor agonists (e.g., bosentan, ambrisentan, macitentan)
 - f) Phosphodiesterase-5 inhibitors (e.g., sildenafil, tadalafil)

- g) Prostaglandin analogues (e.g., alprostadil, epoprostenol)
- h) Riociguat
- 2) Injections of corticosteroids (excluding joint injections)
- 3) Phototherapy
- 4) High-dose intravenous immunoglobulin therapy
- 5) Antibody drugs
- 6) Live vaccines

- Rationale for selection

1) 2) 4) 5)	Established considering the impact on the efficacy of the IP and the safety of participants
3)	Established considering the impact on the efficacy evaluation of the IP
6)	Established considering the safety of participants

- From the day of study treatment initiation to the day of follow-up visit
 - 1) Other drugs and medical devices under development

- Rationale for selection

1)	Established considering the safety of participants and the impact on the efficacy of the IP.
----	--

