9.3.2 Prior and Concomitant Medications and Therapies

9.3.2.1 Prior and concomitant medications

The investigator or subinvestigator will review the following medications for each participant:

- 1) Medications intended to treat SSc
 - Used from 28 days before the day of study treatment initiation to the physical examination at the follow-up visit
- 2) Medications intended to treat adverse events
 - a) Medications intended to treat adverse events of special interest defined in Section 11.6 :
 - Used from the day of study treatment initiation (after initiating study treatment) to the final outcome evaluation.
 - b) Medications intended to treat adverse events except for 1):
 - Used from the day of study treatment initiation (after initiating study treatment) to the physical examination at the follow-up visit.
- 3) All concomitant medications other than 1), and 2)
 - Used from the day of study treatment initiation (after initiating study treatment) to Week 52 or the day of discontinuation visit.

Information to be obtained	Presence or absence of concomitant medications, and the drug name, dosage, drug use classification, start and end dates of use, and indication for use of each concomitant medication
Notes	
The following information is not required to be collected:
 
 • Diagnostic agents, infusions, fluid replacement, nutritional agents, disinfectants, anesthetics for surgery, laxatives and suppository for barium examination (unless these drugs were used for treatment or are included in the prohibited concomitant medications) • Dosage of 3) • Among medications of 1), those newly used in participants who discontinued

	from the study on or after the physical examination at the discontinuation visit.
--	---

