17.1 Analysis Sets

17.1.1 Efficacy Analysis Set (Full Analysis Set: FAS)

The efficacy analysis set includes all participants assigned to treatment except for those who meet any of the following criteria:

- 1) Participants who are found not to have SSc
- 2) Participants who have received no dose of nemolizumab at all after assigned to treatment
- 3) Participants with no efficacy data at all after assigned to treatment

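### Follow-up mRSS mixes off-drug scores with scores on new SSc therapy that the plan does not require to be recorded in discontinued participants

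*Combined protocol and SAP*

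**What the plan says.** **Analysis.** Section 17.3.2 item 1 gives the primary analysis: "Summary statistics will be calculated for mRSS at Week 24 and the change from baseline". Item 2 covers mRSS among the continuous variables: "Summary statistics will be calculated for the following variables and indicators at each time point". Section 9.3.4.1 and Table 9-1 schedule mRSS at the follow-up visit. The full analysis set (Section 17.1.1) leaves out participants without SSc, those never dosed, and a third group: "Participants with no efficacy data at all after assigned to treatment". Use of other therapy is not a ground for exclusion. Section 17.2.1 does not impute missing values, and it maps a discontinuation visit to a scheduled visit only when it falls inside that visit's window.

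**Follow-up visit.** Section 3 says of this visit that the investigator "will evaluate the safety and efficacy after completion of study treatment for all participants". The footnote to Table 9-1 brings discontinued participants back 84 (±7) days after the last dose. Section 11.4 collects adverse events up to that visit.

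**Other therapy.** Section 8.4.3 opens: "Concomitant use of medications and therapies listed below is prohibited in this study". For SSc therapies the ban ends at Week 52 or at the discontinuation-visit examination. Section 5.1 names two of the prohibited items as withdrawal criteria: live vaccines, and "Use of other antibody drugs by Week 52 visit".

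**Recording.** Sections 9.3.2.1 and 9.3.2.2 collect SSc medications and therapies up to follow-up, but the notes list an exception: "Among medications of 1), those newly used in participants who discontinued" from the discontinuation-visit examination onward need not be collected. The same exception applies to non-drug therapies. All three protocol versions in the file carry these notes.

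**The concern.** The protocol itself treats other SSc therapy as a source of distortion. Section 8.4.3 justifies most of the prohibited classes by their effect on efficacy. Section 1.1.2 names cyclophosphamide as the most recommended option for skin thickening and says that "oral corticosteroids are thought to be empirically valid for patients with progressing skin thickening at an early stage". A participant withdrawn for inadequate response has an obvious reason to start such a drug, and that is when recording stops.

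In a single-arm study of 8, follow-up mRSS would be read as showing whether any change persists once nemolizumab is withdrawn. A score taken on another SSc drug does not answer that question. If the start of that drug was never collected, no later analysis can set the score aside.

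**Working it through.** The sample size of 8 is stated to rest on no significance level or power, so there is no figure of the plan's own to reproduce. The check has three parts.

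**1. Does any other route capture the exempted therapy?**
- SSc medications and therapies (item 1 of both sections): collected to follow-up, except for the exempted group.
- Treatment of adverse events: collected to follow-up, but Section 11.2 says that aggravation of the primary disease is not an adverse event. Treatment of worsening SSc need not appear here.
- All other medications (item 3 of Section 9.3.2.1): collection stops at Week 52 or the discontinuation visit.

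No other route fills the gap. Completers' new SSc therapy after Week 52 is recorded, but no analysis in Section 17.3 uses it.

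**2. How long is the interval?**
- Completers: last dose on Day 337, so follow-up is on Day 337 + 84 = 421. Week 52 is Day 365, and 421 − 365 = 56 days pass after the ban ends. Use in this interval is recorded.
- Discontinued participants: if the discontinuation visit comes 28 days after the last dose (one dosing interval, assumed), 84 − 28 = 56 days are unrecorded, or 49 to 63 with the ±7-day window.
- A participant whose last dose is at Week 12 (Day 85) has follow-up on Day 85 + 84 = 169, which is the Week 24 reference day. The mapping rule in Section 17.2.1 concerns only the discontinuation visit, so this score belongs to the follow-up time point and not to Week 24.

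**3. How much can it move the mean?** The shift in the mean is k × s / n, where k participants are on other therapy, s is the mRSS change due to it, and n is the number evaluated. The documents give no s, so I assume 2 to 8 points.

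| n | k | s = 2 | s = 8 |
|---|---|---|---|
| 8 | 1 | 2/8 = 0.25 | 8/8 = 1.00 |
| 8 | 2 | 4/8 = 0.50 | 16/8 = 2.00 |
| 6 | 1 | 2/6 = 0.33 | 8/6 = 1.33 |
| 6 | 2 | 4/6 = 0.67 | 16/6 = 2.67 |

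The chance that at least one of 8 participants is affected is 1 − (1 − p)^8. For p of 5%, 10%, 20% and 30% (assumed; the documents give no rate) it is 34%, 57%, 83% and 94%.

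**The case against.** **Week 24 and Week 52.** A reader might infer that the plan counts mRSS on other therapy as nemolizumab response at these visits. The documents do not support that as a general statement. Other SSc therapy is prohibited up to those visits. Beyond the two named items, withdrawal is open for inadequate response, for significant deviations by sponsor decision, and for any other reason the investigator finds (criteria 6, 10 and 12, numbered as in synopsis Section 6.1). A contaminated value therefore needs a deviation by someone who stays in, or a discontinuation visit inside the window after such therapy. Handling can still be settled in the separate SAP, which is not among the documents supplied, or at the data review (Section 17.5). What remains is that no rule is written and that, in an open-label study, one set at data review would follow sight of the results.

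**Adverse events.** A reader might also infer that late events become uninterpretable. They do not. The investigator judges causality, reviews SSc treatment at each visit (Section 8.4.4), has the medical records, and must give a rationale for calling an event unrelated (Section 11.4). The loss is narrower: anyone working from the trial database cannot make that check.

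**Standing of follow-up mRSS.** It is not a listed endpoint. Section 10.2 names mRSS change at Weeks 24 and 52, and the time-course list omits mRSS. This stands and limits the weight of the point. But the score is collected, efficacy is a stated purpose of the visit, and Section 17.3.2 as written summarises it.

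**Breadth of the exemption.** The notes say that collection is not required, and they cover only therapy newly started from the discontinuation-visit examination onward in discontinued participants. That is correct, but optional recording leaves gaps that nobody can identify afterwards.

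**Conclusion.** The point holds for the follow-up visit. The plan requires mRSS and adverse events from discontinued participants at 84 (±7) days, summarises that mRSS, and waives the one record needed to interpret it. The conflict lies in the text and does not depend on a deviation. Under the written visit mapping, the recording gap does not reach the Week 24 primary endpoint.

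With 8 participants, one affected score moves the follow-up mean by 0.25 to 1.00 points and two move it by 0.50 to 2.00. This rests on an assumed effect of 2 to 8 points and on the assumption that someone discontinues and then starts other SSc therapy. The documents give neither an effect nor a rate. At Weeks 24 and 52 the exposure is contingent, so labelling the values and adding one supplementary summary is enough.

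**What to change.** 1. Delete the two notes in Sections 9.3.2.1 and 9.3.2.2, so that the name and start date of new SSc therapy are collected to follow-up in every participant.
2. Summarise follow-up mRSS separately for participants with and without new SSc therapy. This also puts the completers' records to use.
3. At Weeks 24 and 52, keep the as-observed summary. On the spaghetti plots, flag values obtained after a therapy prohibited in Section 8.4.3 or after an oral steroid dose above the Day 1 dose. Add a summary that omits those values.
4. Do not carry an earlier score forward. That would contradict Section 17.2.1, and because mRSS is scored only at Weeks 4 and 12 between Day 1 and Week 24, it could present a Day 1 score as a Week 24 result.

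Section 9.3.2.1 does not require the dose of medications recorded under item 3, so the steroid flag may be incomplete for steroids given for reasons other than SSc or an adverse event.

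The cost is a few extra medication entries, one extra table and a short addition to the analysis text. The analysis rules can be added at any time before data fixation, but start dates that were never collected may not be recoverable. Permitted therapies and withdrawal rules stay as they are.

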17.3.3 Safety Analysis

The following variables will be summarized on the safety analysis set:

1) Adverse events

The following data will be collected and tabulated for AEs and separately for the treatment-related AEs.

- a) The number of participants included in the safety analysis set, and the number of participants with, and the number of occurrences of AEs, AEs by severity (mild, moderate, and severe), SAEs (total, fatal, and non-fatal), and AESIs will be calculated.
- b) The number of participants with AEs will be calculated by SOC and PT using MedDRA/J.
- c) For AESIs, the number of participants with AESIs, the number of participants with AESIs by PT will be calculated by the category.

2) Laboratory test values

- a) Laboratory test values throughout the treatment period

For the continuous variables, summary statistics will be calculated by laboratory parameter and time point. For the categorical variables, the number of participants will be calculated by category. The percentage of participants will be calculated using the number of observed participants at each time point.

- b) Changes in individual participants during the treatment period

A spaghetti plot will be created for each participant using individual test values by laboratory parameter of continuous variables.

3) Vital signs, physical findings, and other assessments related to safety

- a) Vital signs, electrocardiogram and echocardiography throughout the study period

For the continuous variables, summary statistics will be calculated by vital sign, electrocardiogram parameter, and echocardiography parameter. For the categorical variables, the number and percentage of participants will be calculated by category. The percentage of participants will be calculated using the number of observed participants at each time point.

17.3.4 Analyses of Drug Concentrations and Pharmacokinetic Parameters

The following variables will be summarized on the pharmacokinetic analysis set.

1) Serum concentrations of nemolizumab

- a) Summary statistics including coefficient of variation and geometric mean of serum nemolizumab concentrations will be calculated by time point.
 - b) The serum nemolizumab concentration-time profile will be created using mean serum drug concentrations and their standard deviations.
 - c) The serum nemolizumab concentration-time profile will be created by participant.
 - d) The serum nemolizumab concentration-time profile will be created by participant where participants who tested positive for the first time after study treatment (in blue), those who had tested positive since before treatment (in red), and those who tested negative at all time points (in black) for anti-nemolizumab antibodies in serum in the confirmatory test will be identified by color.
- 2) Pharmacokinetic parameters (C_{max} , t_{max} , $AUC_{0-28Day}$, and AUC_{last})
- Summary statistics including coefficient of variation and geometric mean of parameters will be calculated.

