8.3 Method of Administration

On the days of administration (see Table 9-1: Schedule), the investigator or subinvestigator will subcutaneously inject one DCS (0.6-mL) of nemolizumab slowly to the participant either in the upper arm, abdomen, or thigh. The IP may be administered by a person qualified to administer it under the instruction of the investigator or subinvestigator.

- Precautions

- The IP will be administered after all observation/tests scheduled at the visit have been completed.
- The IP will be administered within the window of the specified visit. However, if the IP cannot be administered within the window, the next dose should be administered 14 days or later after the

previous dose.

- If the participant's body weight is lower than 30.0 kg on the day of administration, the IP must not be administered.

- Rationale for selection>

- 1) Dosage: 60 mg/body Q4W

A phase III study in Japanese patients with atopic dermatitis has demonstrated the long-term safety of nemolizumab 60 mg/body Q4W. This study has been designed to exploratorily evaluate the efficacy of nemolizumab in SSc patients at 60 mg/body Q4W which has shown the long-term efficacy in SSc patients.

- 2) Treatment Period

The treatment period has been set at 52 weeks because long-term observation is required to evaluate the efficacy of nemolizumab on skin thickening in SSc patients in an exploratory manner.

- 3) Day of Follow-up Visit

Considering the serum elimination half-life after a single dose of nemolizumab ranges from 12.6 to 14.6 days in patients with atopic dermatitis, the day of follow-up visit has been set to collect information such as the occurrence of adverse events on the day of 5 times the elimination half-life (84 days \pm 7 days) from the day of the last dose.

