9.1 Schedule of Study Procedures and Assessments

Observation, tests and sample collection will be performed according to the schedule shown in [Table 9-1](#).

Table 9-1: Schedule

Visit	1		2	3	4	5	6	7	8	9	10	11	12	13	14	15	16	17/ discont	FU
Visit name	IC day	Screening	Treatment initiation	W 1	W 2	W 4	W 8	W 12	W 16	W 20	W 24	W 28	W 32	W 36	W 40	W 44	W 48	W 52 or discont	FU ^U
Reference day	-	-14	1	8	15	29	57	85	113	141	169	197	225	253	281	309	337	365/ discont	Day of last dose +84
Visit window	-	- 16/+9	-	±2	±3	±3	±3	±3	±3	±7	±7	±7	±7	±7	±7	±7	±7	±7/ day of discont+14	±7
Screening/management																			
Informed consent	X ^a																		
Physical examinations	X	X	X	X	X	X	X	X	X	X	X	X	X	X	X	X	X	X	X
Demographics	X	X	X																
Body weight		X	X			X	X	X	X	X	X	X	X	X	X	X	X		
Registration		X 1 st	X 2 nd															X Time of discont	
Efficacy evaluation																			
mRSS ^b		X	X			X		X			X			X				X	X
Respiratory function test ^c		X						X			X							X	
Chest HRCT ^d		X									X							X	

Visit	1		2	3	4	5	6	7	8	9	10	11	12	13	14	15	16	17/ discont	FU
Visit name	IC day	Screening	Treatment initiation	W 1	W 2	W 4	W 8	W 12	W 16	W 20	W 24	W 28	W 32	W 36	W 40	W 44	W 48	W 52 or discont	FU ^j
Severity classification of the lung		X									X							X	
ACR-CRIS								X			X							X	
Number of digital ulcers		X	X					X			X			X				X	
Physician's Global Assessment			X					X			X			X				X	
HAQ-DI			X					X			X			X				X	
FACIT-Fatigue			X					X			X			X				X	
FSSG			X					X			X			X				X	
Patient's Global Assessment			X					X			X			X				X	
Safety evaluation																			
Vital signs		X	X	X		X	X	X	X	X	X	X	X	X	X	X	X	X	X
Echocardiography		X									X							X	
Electrocardiogram		X									X							X	
Photography ^e			X																
Laboratory tests																			
Hematology Blood chemistry TARC Urinalysis		X	X	X		X	X	X	X	X	X	X	X	X	X	X	X	X	X
Pregnancy ^f and TB ^g tests		X																	
Hepatitis B and C tests ^h		X						(X)			(X)			(X)			(X)		(X)
Antinuclear antibodies test			X																

Visit	1		2	3	4	5	6	7	8	9	10	11	12	13	14	15	16	17/ discont	FU
Visit name	IC day	Screening	Treatment initiation	W 1	W 2	W 4	W 8	W 12	W 16	W 20	W 24	W 28	W 32	W 36	W 40	W 44	W 48	W 52 or discont	FU ¹
PK analysis and immunogenicity																			
Serum nemolizumab concentrations			X	X	X	X	X	X	X	X	X			X				X	X
Anti-nemolizumab antibody assay			X								X			X				X	X
Biomarkers																			
IL-31			X			X	X	X	X	X	X			X				X	

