ⁱ To be administered after all observation/tests are performed. If the IP cannot be administered within the window indicated, the next dose should be administered 14 days or later after the day of the previous dose.

^j Participants who discontinued the study will visit the site 84 days (± 7 days) after the day of the last dose of study treatment for observation/tests at FU shown in [Table 4-1](#). Participants discontinued the study before study treatment initiation need not to undergo observation/tests scheduled on the day of visit for discontinuation.

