13.1 Pharmacokinetic Measurements

1) Variable to be measured

Serum concentration of nemolizumab

2) Collection of blood samples

Blood samples will be collected on the day of study treatment initiation, at Week 1, 2, 4, 8, 12, 16, 20, 24, and 36, Week 52 or on the day of visit for discontinuation, and on the day of follow up. On the days of study treatment, blood samples will be collected before administration of IP.

The collected blood samples will be centrifuged to separate the serum, and the serum samples will be stored frozen until measured. The amount of blood collected, centrifugal conditions, and storage conditions are specified in a separate operating procedure.

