17.2 Data Handling

17.2.1 Common Rules

- a) Handling of missing values
The missing values will not be imputed.
- 2) Handling of data on the day of visit for discontinuation
The data measured or evaluated on the day of visit for discontinuation will be handled as the data of the relevant evaluation period if the visit is within the allowance of any visit for evaluation period. However, such data will not be included in the analysis if another data has been obtained in the relevant evaluation period.

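### By-visit concentration summaries ignore time since last dose, although the windows allow 14 to 42 days at Weeks 24, 36 and 52 and a discontinuation sample taken after a missed dose can be pooled as on treatment

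*Combined protocol and SAP*

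**What the plan says.** All sections are in the combined protocol and SAP, and read the same in each protocol version it contains.

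- **Summary (17.3.4 1) a) and b)).** "Summary statistics including coefficient of variation and geometric mean of serum nemolizumab concentrations will be calculated by time point". A mean profile with standard deviations follows.
- **Sampling (13.1).** Blood is drawn on the day treatment starts, "at Week 1, 2, 4, 8, 12, 16, 20, 24, and 36, Week 52 or on the day of visit for discontinuation", and at follow-up. On dosing days it is drawn before the injection.
- **Windows (9.1, Table 9-1).** Visits are anchored on Day 1. The windows are ±3 days for Weeks 2 to 16 and ±7 days from Week 20. The last treatment-period column allows ±"7/ day of discont+14".
- **Dosing (8.3).** "The IP will be administered within the window of the specified visit". For a dose that cannot be given in its window, a footnote to Table 9-1 says "the next dose should be administered 14 days or later after the day of the previous dose".
- **Discontinuation data (17.2.1 2)).** Results from that visit "will be handled as the data of the relevant evaluation period if the visit is within the allowance of any visit for evaluation period", unless the period already has a result. Section 17.2.2, on pharmacokinetic data, covers values below the quantification limit, missing values and non-calculable parameters. It does not override this rule and sets no condition on time since dosing.

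**The concern.** A pre-dose concentration is interpretable as a trough only if the time since the previous dose is known and reasonably constant. Here both the dose and the next sample can move within their windows, and the summary groups the results by visit. The reported CV would then mix visit timing with real differences between participants.

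The discontinuation rule raises a different problem. It fills an empty visit with whatever sample falls in that window, so a participant who has stopped dosing can contribute a washout concentration to an on-treatment mean.

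Pharmacokinetics is part of the secondary objective (Section 2.2) and the target is 8 participants (Section 17.4.1), so one mistimed value can move a summary. After baseline, antibodies are measured only at Weeks 24, 36, 52 or discontinuation, and follow-up (Section 14.1). The scheduled on-treatment antibody results therefore all fall at visits with the widest dose-to-sample range.

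**Working it through.** The plan states no figure for timing-related spread, so there is none to reproduce.

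**Inputs from the documents.** Reference days and windows come from Table 9-1: Week 12 is Day 85, Week 16 Day 113, Week 20 Day 141 and Week 24 Day 169. The half-life of 12.6 to 14.6 days is from Section 8.3 (single doses, atopic dermatitis).

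**Assumptions.** First-order elimination, one compartment, and tmax 3 to 8 days. The documents give neither a tmax nor a half-life for SSc.

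**1. Compliant dose-to-sample interval** = 28 ± (window of the dose visit + window of the sample visit).

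| Sample | Windows (days) | Interval (days) |
|---|---|---|
| Week 4 | 0 + 3 | 25 to 31 |
| Weeks 8, 12, 16 | 3 + 3 | 22 to 34 |
| Week 20 | 3 + 7 | 18 to 38 |
| Weeks 24, 36, 52 | 7 + 7 | 14 to 42 |

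**2. Extreme spread at Week 24.** The concentration is the sum over doses of ka/(ka − k) × [exp(−k·d) − exp(−ka·d)]. Here d is days since each dose, k = ln 2/half-life, and ka solves tmax = ln(ka/k)/(ka − k). The first five doses stay on their reference days. The Week 20 dose and the Week 24 sample move to the limits of their windows:

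- Shortest: dose Day 148, sample Day 162 (14 days).
- Longest: dose Day 134, sample Day 176 (42 days).
- Reference: dose Day 141, sample Day 169 (28 days).

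| Half-life (days) | tmax (days) | Shortest/reference | Longest/reference | Ratio of extremes |
|---|---|---|---|---|
| 12.6 | 4 | 2.01 | 0.51 | 3.95 |
| 12.6 | 7 | 1.95 | 0.51 | 3.83 |
| 14.6 | 4 | 1.80 | 0.57 | 3.17 |
| 14.6 | 7 | 1.77 | 0.57 | 3.11 |

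Over tmax 3 to 8 days the factors are 1.7 to 2.0 and 0.51 to 0.57. The ratio runs from 3.04 to 3.95, cut to one decimal as about 3.0 to 3.9.

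**3. Typical spread at Week 24.** Visit days were simulated 16,000 times, without an absorption phase. Uniform use of the full windows gives a timing-only CV of 26% to 31% and a median max/min among 8 participants of 2.1 to 2.4. With windows about half used, the CV is 12% to 14% and the max/min 1.4 to 1.5.

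**4. Discontinuation sample after a missed dose.** Take the last dose at Week 12 (Day 85), no Week 16 dose, and a discontinuation visit on Day 139. That day lies in the Week 20 window (141 ± 7 = Days 134 to 148). Time since dose is 139 − 85 = 54 days, against at most 38 by design. Relative to 28 days, the factor is 2^(−26/12.6) = 0.24 to 2^(−26/14.6) = 0.29.

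If the other seven participants all sat at the 28-day value, this one sample would:

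- lower the mean to (7 + 0.24)/8 = 0.91 (also 0.91 with 0.29);
- lower the geometric mean to 0.24^(1/8) = 0.84 or 0.29^(1/8) = 0.86;
- raise the CV from 0 to (0.76/√8)/0.905 = 30% or (0.71/√8)/0.911 = 28%.

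**The case against.** **Size.** A reader might infer a spread of about 4-fold or more, since 2^(28/14.6) = 3.8 and 2^(28/12.6) = 4.7. That shortcut shifts the carry-over from earlier doses by the same 14 days each way. With all doses on schedule, it would put the sample on Day 155 or Day 183, outside the Week 24 window of Days 162 to 176. Even 3.0 to 3.9 needs one participant dosed late and sampled early, and another the reverse, each by the full 7 days. This objection stands, and the typical spread is much smaller.

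**Discontinuation.** A reader might also infer that off-drug samples add to that fold figure. They do not. If no dose was missed, a discontinuation sample lies in the same interval range as any other. Harm needs a missed dose and a visit falling in a window with no other result. In the example, the 14-day limit puts the decision to discontinue on or after Day 125. That is uncommon, but the rule as written permits it.

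**Relevance.** No trough parameter, accumulation analysis or exposure-response analysis is planned, and nothing is tested. Antibody colours in 17.3.4 1) d) are set by the confirmatory test, so misreading a low value as antibody-driven clearance is a risk of interpretation and not a planned inference. Individual profiles are planned, and the plan does not say that they use nominal time, so it cannot be faulted for doing so.

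**Text not seen.** Section 17 defers details to a separate SAP, and Section 17.5 lets the pre-lock data review settle data handling. Either may define time points by actual days since dose. If so, confirming it closes the point.

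**Conclusion.** The concern holds in two separate parts.

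1. **Windows.** The 14 to 42 day range at Weeks 24, 36 and 52 is exact arithmetic from Table 9-1. The Week 24 consequence is at most about 3.0 to 3.9-fold, with only the last dose and the sample shifted, and typically 1.4 to 2.4-fold among 8 participants. The practical harm is a CV that includes timing noise.
2. **Discontinuation rule.** Where a dose was missed, Section 17.2.1 2) can put an off-drug concentration at 0.24 to 0.29 of the 28-day trough into an on-treatment summary. This is the part where a stated rule gives a wrong result.

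The sizes depend on a half-life taken from another disease. Section 8.3 also equates 84 days with five half-lives, whereas 5 × 12.6 to 5 × 14.6 is 63 to 73 days. At 84/5 = 16.8 days the extreme spread falls to about 2.6-fold. The interpretation of descriptive pharmacokinetics is affected; no test or efficacy result is.

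**What to change.** - **17.2.1 2) and 17.2.2.** Exempt concentrations from the discontinuation rule when a scheduled dose was missed, that is, when days since the last dose exceed what the windows allow for that visit: 31 at Week 4, 34 at Weeks 8 to 16, 38 at Week 20, and 42 at Weeks 24, 36 and 52. List these values by days since last dose and leave them out of the by-visit mean, CV and geometric mean.
- **17.3.4 1) a) and b).** Keep the by-visit summary of all remaining samples. Add a supplementary summary, with n shown, of samples taken within a pre-stated interval around 28 days after the previous dose, for example ±7 days.
- **17.3.4 1) c) and d).** State that individual and antibody-coloured profiles use actual days, with dose dates marked.

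Visit dates and dosing status are already in the CRF (Section 19.1.1, items 2 and 26), so the cost is SAP wording and a small extra analysis. The narrower summary should not replace the main one. If the ±7-day windows are used uniformly, 15 × 15 = 225 combinations of dose day and sample day are equally likely. A ±3-day band keeps 93/225 = 41%, about 3 of 8, and a ±7-day band keeps 169/225 = 75%, about 6 of 8. As a supplement, the lower n affects that table only.
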